## 15.2.1.2 Safety Population/Intent-to-Treat (ITT) Population

The Safety Population will include all subjects who receive at least one dose of study medication. The ITT Population will be identical to the Safety Population for this study. All baseline characteristics, demographic and efficacy endpoint data will be presented using the ITT Population.

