# 15.2.2 Safety Analyses

All safety endpoints will be evaluated using the Safety Population.

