## Safety Population / Intent-to-Treat (ITT) Set:

The Safety Set will include all subjects who receive at least one dose of study medication. The ITT Set will be identical to the Safety Set for this study. All baseline characteristics, demographic and efficacy endpoint data will be presented using the ITT Set.

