## Adverse Events Summary

An AE data listing of all AEs collected on study, including verbatim term, preferred term, treatment, severity, and relationship to treatment will be provided. Serious Adverse Events (SAEs), adverse events of special interest, and details of subjects withdrawing due to adverse events will also be listed. The start day (relative to the first dosing day), and the duration of AEs will be included in listings.

A topline summary for Part A, Part B, and Overall will present the number of events and the number of subjects by randomized dose level and by cohort with:

- any TEAE
- any TEAE considered as related to study drug (evaluated by the investigator as Unlikely Related, Unrelated, Possibly Related, Probably Related, Definitely Related, or Unknown)
- any serious TEAE
- Maximum severity TEAE of mild, moderate, severe, life threatening, and death; i.e. a subject with TEAEs at different intensities will be summarized at the most severe intensity
- any TEAE of special interest
- any TEAE leading to study drug discontinuation
- any TEAE leading to death

The table will also include the total number of TEAEs reported in each cohort and overall. The total number of unique terms within subjects will also be presented, counting each TEAE only once within each subject.

Additionally, the following will be tabulated with the number of events and the number/percent of subjects by randomized dose level in each cohort, and by cohort. Summaries will be ordered by descending order of event count in the overall column. All summary tables will be presented by study part and over the whole study, where AEs will be categorized by the Part in which the AE started i.e. an AE which began during the Part A Core Study Phase will be categorized under Part A even if it continues into Part B (unless it increases in severity).

- TEAEs by SOC and preferred term
- TEAEs by preferred term

• TEAEs regarded as at least possibly related to study drug by SOC and preferred term

The following will also be tabulated with the number/percent of subjects by randomized dose level in each cohort and by cohort:

- TEAEs and Serious AEs by SOC, preferred term, and maximum severity
- TE AESIs by SOC, preferred term, and maximum severity if applicable
- TE AESIs (regarded as at least possibly related to study drug) by SOC, preferred term, and maximum severity

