## 5.3.1 Red Blood Cell (RBC) Transfusions

The absolute and change in number of RBC transfusions per month will be tabulated using descriptive statistics by randomized dose group, by cohort, by phase of the study (Baseline, Part A Core Study Phase and Part B Long Term Extension Phase) and over the whole on-treatment study parts (Part A and Part B combined).

Summary statistics will be presented by study phase as follows:

- Baseline:
  - Number of Transfusions and Units per month for the *n* subjects who had at least 1 infusion in the 365 days prior to first study dose
  - Number of Transfusions and Units per month for the N subjects in the dose group (i.e. all subjects in the dose group, regardless of receiving transfusions prior to enrollment)
- Post-Baseline Study Phases (Part A, Part B, Part A and B combined):
  - Number of Transfusions and Units per month for the *n* subjects who had at least 1 infusion in the respective phase
  - Number of Transfusions and Units per month for the N subjects in the dose group (i.e. all subjects in the dose group, regardless of receiving transfusions during the respective phase)
  - Change from Baseline of the Number of Transfusions and Units for the N subjects in the dose group (i.e. all subjects in the dose group, regardless of receiving transfusions during the respective phase)

Only whole blood and Packed Red Blood Cell (PRBC) transfusions will be included.

The number of RBC transfusions per month will be calculated for each part of the study as:

RBC transfusions per month

number of transfusion reported during study part \* 28 number of days in that part of study

The whole on-treatment study will be from first dose to last dose received. A similar calculation will be used for the number of units transfused per month.

The baseline number of transfusions per month will be calculated as number of transfusions reported on 12-month transfusion history /12.

All 12-month transfusion history and on study transfusion data will be listed by Cohort. A separate listing of the number of transfusions per month and number of units transfused per month for baseline, each part and over the whole on-treatment study parts will also be included.

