## 2. INTRODUCTION

This Statistical Analysis Plan (SAP) is prepared to provide a more technical and detailed elaboration of the principal statistical features stated in the protocol. The SAP will ensure that the tables, listings, and figures that will be produced and statistical methods that will be used for the final analysis are complete and accurate and will allow valid conclusions to be drawn.

In the development of this final analysis SAP, the following study documents were used:

- Protocol Number (Version 1.0 Amendment 4), 17 Jan 2019
- Electronic Case Report Form (eCRF), extracted 18 Oct 2021
- Medical Coding Guidelines (Version 5.0), 10 Sep 2021

The study protocol consists of two study parts for analysis (details of the scheduled assessments of the study parts can be found in Section 3.3 of the SAP):

- Core Study Phase (Part A): the study period of the daily 270/280 mg or 360 mg APL-2 dose regimen.
- Long Term Extension Phase (Part B): the study period of the twice or three times weekly 1080 mg APL-2 dose regimen.

Statistical Analysis Plan Version 1.0 was used for the production of the Interim Part A Core Study Phase Analysis. This SAP will present the results for the final analysis for subjects who rolled over into Part B, presenting the safety and efficacy results of Part B and Part A + B as whole completed study as well. Definitions for the study days and baselines are outlined in Section 4. Details of the planned analyses are outlined in Section 5.

In the event that a discrepancy is found between the descriptions in the statistical section of the protocol and this document, the description in this document supersedes the descriptions in the statistical section of the protocol. Any deviations from the final analysis plan or from what is outlined in the protocol will be discussed in the final study report.

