#### Safety Set / Intent-to-Treat (ITT) / Pharmacodynamic (PD) Set:

Safety Set will only include the subjects who roll over to Part B and receive at least one dose of 1080 mg APL-2.

ITT Set and PD Set will be identical to the Safety Set for this study.

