# 5. STATISTICAL ANALYSIS METHODOLOGY

In general, tables will be presented by cohort (Cohort 1 wAIHA / Cohort 2 CAD) and study part (Part A + B / Part B). The Part B summaries will start from Study Day 1 in Part B through the end of the Part B Long Term Extension Phase, while Part A + B will start from Study Day 1 in Part A through the end of the Part B Long Term Extension Phase.

Tabulations for continuous data will use a standard set of descriptive statistics for the results and for change from baseline, as specified: number of observations available (n), mean, standard deviation (SD), median, and range (minimum, maximum). Change from Baseline for Part A + B summaries will calculate the Change from Part A Baseline summary statistics. Change from Baseline for Part B summaries will calculate the Change from Part B Baseline summary statistics.

Categorical or dichotomous data will be tabulated using frequencies (counts and percentages). The numerator and denominator for each percentage calculation will be specified in the footnotes of table shells. Categorical data will be populated as appropriate for each study part (Part A + B and Part B).

Data listings will present all information recorded in eCRFs for all subjects and visits. All listings will be sorted by cohort and subject number.

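### The Part B SAP applies the names Safety and ITT to 1080 mg rollovers only and runs the Part A + B tables on them, so the final plan text shows no all-treated whole-study summary of TEAEs or transfusions

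*SAP*

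**What the plan says.** There are two SAPs, dated 27 April 2020 (the 2020 SAP) and 8 November 2022 (the Part B SAP).

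- **Protocol 15.2.1.2 and 15.2.2.** "The Safety Population will include all subjects who receive at least one dose of study medication", and ITT is the same group. "All safety endpoints will be evaluated using the Safety Population".
- **2020 SAP 4.2, 5.2.1 and 5.3.1.** "The Safety Set will include all subjects who receive at least one dose of study medication", again with ITT identical. On that set it plans "A topline summary for Part A, Part B, and Overall will present the number of events and the number of subjects", and a transfusion summary over both parts combined.
- **Part B SAP 4.1.** "Safety Set will only include the subjects who roll over to Part B and receive at least one dose of 1080 mg APL-2". The ITT and PD Sets are made identical to it.
- **Part B SAP 2.** The final analysis is for subjects "who rolled over into Part B, presenting the safety and efficacy results of Part B and Part A + B as whole completed study". The same section gives this SAP precedence over the protocol's statistical section.
- **Part B SAP 5.** "Part A + B will start from Study Day 1 in Part A through the end of the Part B Long Term Extension Phase".
- **Part B SAP 5.2.1.2 and 5.2.1.6.** TEAEs are summarised by study part in the Safety Set. The overall table has rows for TEAEs leading to discontinuation and to death. Exposure-adjusted incidence (defined in 5.2.1.4) is planned for four tables: non-injection-site, related, injection-site and serious events.
- **Part B SAP 5.3.1.4.** The Part A + B transfusion tables use the ITT and Per Protocol Sets, limited further to subjects with a transfusion at baseline or on study.

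**The concern.** The primary endpoint is the incidence and severity of TEAEs. The Part A + B tables report it from the first Part A dose, but only in subjects who stayed on treatment long enough to receive 1080 mg. Entry to the set depends on what happened after the counting starts, and the outcome that most directly prevents entry, a TEAE that kills or ends treatment, is itself a row of the table.

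The set still carries the names that the protocol and the 2020 SAP use for all dosed subjects. A reader who sees Part A + B and Safety Set in a table title could take it as the whole-study safety result. The Overall TEAE and combined transfusion summaries that the 2020 SAP planned on all dosed subjects do not reappear in the available text of the Part B SAP. Its planned-table list was not available for this check.

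**Working it through.** The plan states no figure that bears on this point, so there is nothing to reproduce. Step 1 is set logic. Steps 2, 3 and 5 are illustrations on assumed counts.

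**1. Membership against counting period**

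| | Who is in the set | Counting starts |
|---|---|---|
| Protocol 15.2.1.2; 2020 SAP 4.2 | any dose of APL-2 | first dose |
| Part B SAP, Part B tables | at least one 1080 mg dose | first 1080 mg dose |
| Part B SAP, Part A + B tables | at least one 1080 mg dose | first Part A dose |

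Only the last line mixes a later entry condition with an earlier start. Death or permanent discontinuation before 1080 mg rules out the 1080 mg dose and hence membership. The contribution of such subjects to every Part A + B TEAE row is exactly zero.

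**2. Discontinuation or death row**

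Inputs: 12 per cohort (the target in Part B SAP 3.3). Assumptions: d subjects with such a TEAE before 1080 mg, no other non-rollovers, and no such event after 1080 mg. The plan shows 0/(12 − d); all treated shows d/12.

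| d | Part A + B as planned | All treated |
|---|---|---|
| 1 | 0/11 | 1/12 = 8.3% |
| 2 | 0/10 | 2/12 = 16.7% |
| 3 | 0/9 | 3/12 = 25.0% |
| 4 | 0/8 | 4/12 = 33.3% |

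**3. Exposure-adjusted serious AEs**

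Formula (Part B SAP 5.2.1.4): subjects with an event × 100 / sum of times to onset in years. Subjects without the event are censored at last dose + 56 days − first dose + 1.

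Assumptions: 20 rollovers, first 1080 mg on Day 336, 336 days of Part B (last dose Day 671, censored at 727 days), and 5 of the 20 with a first event on Day 336. Four non-rollovers stop on Day 150; s of them have an event on Day 140 and the rest are censored at 206 days.

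- As planned: (15 × 727 + 5 × 336)/365.25 = 12,585/365.25 = 34.5 years; 500/34.5 = 14.5 per 100 person-years.
- All treated, s = 0: (12,585 + 4 × 206)/365.25 = 36.7 years; 500/36.7 = 13.6.
- All treated, s = 4: (12,585 + 4 × 140)/365.25 = 36.0 years; 900/36.0 = 25.0.
- For s = 1, 2, 3: 16.4, 19.3, 22.1.

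The ratio of planned to all-treated runs from 1.07 to 0.58. With 168, 672 or 1176 days of Part B it runs 1.08–0.59, 1.05–0.57 and 1.03–0.57. The set drops both the events and the person-time of non-rollovers, so the direction is not fixed.

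**4. Can the two reports be added?**

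For fatal and treatment-ending rows, largely yes: Part A events of all dosed subjects are in the Part A table. The TEAE window differs, 30 days after last dose in the 2020 SAP (5.2.1) against 56 in the Part B SAP (5.2.1.1).

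For the any-TEAE, serious and maximum-severity rows, no, because rollovers' Part A events are in both reports. Setting the window difference aside, suppose the serious row reads 3/12 in the Part A table, 3/10 in Part A + B and 2/10 in Part B. Rollovers with a Part A event may number 1, 2 or 3. That leaves 2, 1 or 0 non-rollovers with an event, so the all-treated count is 5, 4 or 3 of 12 (41.7%, 33.3% or 25.0%). The columns alone do not identify it.

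**5. Transfusions**

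Assume 24 treated, 4 non-rollovers at 0.5 per month, 20 rollovers at 0.1, and all meeting the transfusion condition in 5.3.1.4. As planned the mean is 0.10; all treated gives (20 × 0.1 + 4 × 0.5)/24 = 0.17. If non-rollovers had fewer transfusions, the sign would reverse.

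**6. A subject in neither report's summary tables**

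Part B SAP 3.3 lets a subject enter Part B on the Part A dose until the sorbitol formulation is available. If that subject stops before 1080 mg, 2020 SAP 4.5 cuts the Part A data at Visit 15, and Part B SAP 4.1 excludes the subject. Later TEAEs then appear to fall in no summary table.

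**The case against.** The strongest reply is that nothing is hidden. Part B SAP 2 confines the final analysis to rollovers in the same sentence that calls Part A + B the whole study, and it takes precedence over the protocol's statistical section. A rollover set is normal for an extension report. The Part A analysis tabulates all dosed subjects (2020 SAP 4.5, 5.2.1). Disposition with reasons covers all enrolled subjects (Part B SAP 5.1.1). The AE, SAE and withdrawal listings (5.2.1.5, read with 5 and 6.4.3) appear to cover every non-screen-failure subject. With at most 24 subjects, a reader could rebuild the counts by hand. The study is a descriptive pilot.

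All of that stands, and it rules out several stronger readings that a reader might infer:

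- *Early deaths or discontinuations vanish from reporting.* They do not; they are in the Part A tables and, apparently, the final listings.
- *The discontinuation or death row must read zero.* Only the contribution from before 1080 mg is zero; later events in rollovers count.
- *The final TEAE rates are biased downward.* Step 3 shows either direction.
- *An exposure-adjusted rate of discontinuation or death is diluted by event-free Part A time.* No such rate is planned.
- *The different MedDRA versions (20.0 and 23.0) block adding the any-TEAE, serious or severity rows.* Version affects only SOC/preferred-term and unique-term tables.
- *The redefinition was unauthorised.* The precedence clause permits it.

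One uncertainty remains. Part B SAP 4.2.3 puts subjects with Part A Visit 16/17 assessments into safety summaries. Its target days, 420 and 504, lie 84 and 168 days after Visit 15; the protocol's follow-up visits are on Days 378 and 420. The sentence could mean subjects still on the Part A dose after Visit 15 or subjects in follow-up, and does not say how either fits the section 4.1 set.

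Disclosure and listings do not supply a tabulated all-treated whole-study summary, and a rollover set suits Part B tables, not tables that start at the first Part A dose.

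**Conclusion.** The point holds as a problem of selection and labelling and should be fixed. As written, Part A + B TEAE tables exclude any contribution from subjects who died or stopped permanently before 1080 mg, and Part A + B transfusion tables leave out those subjects' transfusions. Part A visits in the Part A + B efficacy displays carry the same selection; Part B visit means do not.

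That exclusion follows from the definition and needs no assumption. Its size depends on the number of non-rollovers, which the documents do not state. With none, there is no bias. Under the step 2 assumptions the gap in the treatment-ending row is 8.3 to 33.3 percentage points per cohort. Under the step 3 assumptions the planned serious-AE rate of 14.5 per 100 person-years compares with 13.6 to 25.0 for all treated. The absence of an all-treated Part A + B summary is judged on the available text, without the planned-table list.

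**What to change.** - Run the Part A + B TEAE, exposure-adjusted incidence and transfusion tables on all subjects with at least one dose of APL-2, with one TEAE window and one MedDRA version across them.
- Rename the section 4.1 set, for example Part B 1080 mg Set, and keep it for Part B-only tables.
- In Part A + B efficacy displays, show n at each visit and note that Part B visits contain rollovers only.
- State how subjects who continue the Part A dose after Visit 15 and never receive 1080 mg are counted, and whom the Visit 16/17 sentence in 4.2.3 covers.

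The cost is SAP wording, recoding of non-rollovers' adverse events to the later dictionary, and reruns of existing programs on data already collected. The drawback is an n that varies by visit in the Part A + B displays.

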#### Per Protocol (PP) Set:

PP Set will only include subjects who were in the PP set in Part A and roll over to Part B and have not violated any inclusion or exclusion criteria and/or deviated from the protocol in a way that could influence their efficacy assessment while on study in Part B.

The PP Set will be used in efficacy analyses for Part B and Part A + B.

Decisions concerning the exclusion of subjects from the PP sets will be made and documented during an adjudication by DPC and the sponsor prior to database lock.

#### Pharmacokinetic (PK) Set:

The PK Set will only include all subjects in the Safety Set who rolled over into Part B and have at least one evaluable non-BLQ post-dose PK measurement.

#### 4.2 Definitions

#### 4.2.1 Study Day

#### Part A + B:

Study Day 1 for Part A + B will be the day a subject takes the first dose of APL-2, which will be calculated as:

For events that occurred on the day of or after administration of the first APL-2 dose:

Part A + B Study Day = visit date – date of first APL-2 dose + 1

For events that occurred on days before administration of the first APL-2 dose:

Part A + B Study Day = visit date – date of first APL-2 dose

## Part B:

Part B is considered all visits and assessments from the date of first 1080 mg APL-2 dose through the date of last APL-2 dose.

For events that occurred on the day of or after administration of the first 1080 mg APL-2 dose in Part B Long Term Extension Phase:

Part B Study Day = visit date - date of first 1080 mg APL-2 dose + 1

For events that occurred on days before administration of the first 1080 mg APL-2 dose:

Part B Study Day = visit date – date of first 1080 mg APL-2 dose

#### 4.2.2 Baseline and Change from Baseline

Summary tables will present: 1) change from Part A baseline summaries assessments during Part A + B and 2) change from Part B baseline

Apellis Pharmaceuticals, Inc. Protocol: APL2-CP-AIHA-208 Part B Long Term Extension Statistical Analysis Plan

Version 1.0

summaries assessments during Part B. This section outlines the definitions for baseline and change from baseline for all safety and efficacy assessments collected during study visits, except for transfusions (see Section 5.3.1).

#### Part A + B

The baseline for Part A + B summaries will be the Part A Baseline. Unless indicated otherwise Change from Part A+ B Baseline (Part A + B CFB) will be calculated as follows:

> Part A + B CFB = Visit Result – Part A Baseline Result

Percent Change from Part A + B Baseline (Part A + B PCFB) will be calculated as follows:

Part A + B PCFB (%) = 100\*(Visit Result – Part A Baseline Result)/ (Part A Baseline Result),

where Part A baseline is the last assessment prior to the first APL-2 dose in Part A.

#### Part B

Part B baseline for this study will be derived as the last measure prior to the first 1080 mg APL-2 dose.

Unless indicated otherwise Part B change from baseline (Part B CFB) will be calculated as follows for after Part B Study Day 1:

Part B CFB = Visit Result – Part B Baseline Result

Percent change from baseline (Part B PCFB) will be calculated as follows:

Part B PCFB (%) = 100\*(Visit Result – Part B Baseline Result)/ (Part B Baseline Result) Where Part B Baseline is the last assessment prior to the first 1080 mg APL-2 dose on Part B Study Day 1.

#### 4.2.3 Visit Windowing Based on Study Day

Data will be summarized and analyzed based on the list of visits specified in table below for Part A + B and the Part B. The relative day will be used to assign analysis visit following the table below. All the records post-baseline will be assigned to an appropriate analysis visit using the following:

For the post-baseline visits, the lower and the upper bound for the analysis visit windows are defined as the midpoints of the target date of the scheduled visits. If the date of assessment falls in between the lower bound and the upper bound for a visit as specified in the schedule of assessments of the protocol, then it will be assigned to that visit. If the interval separating 2 scheduled visits is an even number of days, the middle day will be included in the lower bound of the next visit. If more than 1 record is within the same analysis visit window, the record closest to the midpoint of the interval will be used in the analysis. If 2 records are tied before and after the middle of the interval, the earlier record will be used in the analysis. If more than one assessment (including the early termination or unscheduled assessments) falls within the same defined window, the assessment closest to the target day with non-missing data will be considered for analysis.

In listings that are presented by visit, windowed assessments that are used in the analysis tables by visit will be identified.

Part	Study Visit	Target Day	Analysis Window	Interval
Part A + B	Part A Visit 1 (Screening)	Part A+B Study Day -30	<1*	NA
	Part A Visit 2 (Baseline)	Part A+B Study Day 1	1*	1
	Part A Visit 3 (Day 2)	Part A+B Study Day 2	2	1
	Part A Visit 4 (Day 3)	Part A+B Study Day 3	3	1
	Part A Visit 5 (Day 7)	Part A+B Study Day 7	>=4-<11	7

Table 1: Visit Windowing for Part A + B Analyses

Apellis Pharmaceuticals, Inc.
-------------------------------

Part B Long Term Extension Statistical Analysis Plan   Version 1.0   08 Nov 2022					
	Part A Visit 6 (Week 2)	Part A+B Study Day 14	11-<21	10	
	Part A Visit 7 (Week 4)	Part A+B Study Day 28	21-<42	21	
	Part A Visit 8 (Week 8)	Part A+B Study Day 56	42 - <70	28	
	Part A Visit 9 (Week 12)	Part A+B Study Day 84	70 - < 98	28	
	Part A Visit 10 (Week 16)	Part A+B Study Day 112	98 - < 126	28	
Part A + B, cont.	Part A Visit 11 (Week 20)	Part A+B Study Day 140	126 - < 154	28	
	Part A Visit 12 (Week 24)	Part A+B Study Day 168	154 - < 196	42	
	Part A Visit 13 (Week 32)	Part A+B Study Day 224	196 - < 252	56	
	Part A Visit 14 (Week 40)	Part A+B Study Day 280	252 - < 308	56	
	Part A Visit 15 (Week 48)	Part A+B Study Day 336	308 - < 378	70	
	Part A Visit 16 (Week 60)	Part A+B Study Day 420	378 - < 462	84	
	Part A Visit 17 (Week 72)	Part A+B Study Day 504	462 - < 546	84	
	Subjects who had assessments at Part A Visit 16/17 are included in safety summaries but not efficacy summaries.				
	Part B Baseline (Day 1)	Date of First 1080 mg Dose = Part B Study Day 1	≤ Part B Study Day 1*	NA	
	Part B Transition Visit 1 (Day 7)	Part B Study Day 7	> Part B Study Day 3 - < Part B Study Day 11	7	
	Part B Transition Visit 2 (Week 2)	Part B Study Day 14	Part B Study Day 11 - < Part B Study Day 21	10	
	Part B Transition Visit 3 (Week 4)	Part B Study Day 28	Part B Study Day 21 - < Part B Study Day 56	25	
	Part B Visit 1 (Week 12)	Part B Study Day 84	Part B Study Day 56 - Part B Study Day < 126	70	
	Part B Visit 2 (Week 24)	Part B Study Day 168	Part B Study Day 126 - Part B Study Day < 210	84	
	Part B Visit 3 (Week 36)	Part B Study Day 252	Part B Study Day 210 - Part B Study Day < 294	84	
	Part B Visit 4 (Week 48)	Part B Study Day 336	Part B Study Day 294 - Part B Study Day < 378	84	
	Part B Visit 5 (Week 60)	Part B Study Day 420	Part B Study Day 378 - Part B Study Day < 462	84	
	Part B Visit 6 (Week 72)	Part B Study Day 504	Part B Study Day 462 - Part B Study Day < 546	84	
